## Overview study devices and supplies

### Investigational center staff will disburse to the following subjects as needed:

- Guardian™ Sensor (3)(s)
- BG supplies (e.g. batteries, meter strips, lancet holder and lancets)
- Other study supplies and adhesives (e.g. alcohol swabs, Oval tape, Hypafix™\* tape, Tegaderm™\* dressing, Skin Tac™\* Wipe) as needed

Investigational center staff will record and track all study devices outlined in device accountability section (see Section 6.4) on the appropriate eCRF.

### Investigational center staff will:

- Remind subjects to perform fingersticks (capillary SMBG)
- Remind subjects to contact the 24-Hour TS for technical issues and support
- Will follow the Discharge Criteria Guidelines
- Fingerstick will be performed at home as stated in 9.2.2.3.1.

### Hydration:

- In order to avoid ketosis, subjects will be encouraged to ingest unlimited sugar free fluids to maintain hydration.

### **Meals/Medication:**

- During the in-clinic YSI™\*/SMBG FST, subjects should continue to eat and take diabetes medications and meals as per their usual diabetes management and investigator discretion.

### **Insulin Administration:**

- During the in-clinic YSI™\*/SMBG FST, subjects should take their insulin as per their usual diabetes management and investigator discretion

### **Exercise:**

Subjects are required to begin exercise at start of YSI™\*/SMBG FST if their glucose is between 100-300 mg/dL mg/dL. They should continue exercise for at least 60 minutes. This exercise can be in the form of playing or moving around. We recommend the sites provide toys and games for young subjects to use during the exercise period. However, exercise should be stopped, and meal administered and/or glucose given when:

- Glucose is less than or equal to 70 mg/dL for subjects 2-6 years of age
- Glucose is less than or equal to 65 mg/dL for subjects 7-13 years of age

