Starting Rules for Subjects:	
The start of the YSI™*/SMBG FST:
 

○ With challenge can occur if subject's ketone level is less than or equal to (<math>\leq</math>) 0.6 mmol/L.

 
For example, should a subject arrive with ketone levels greater than (<math>></math>) 0.6 mmol/L, per investigator discretion, IV or oral hydration may be provided to subject to bring ketone level less than or equal to (<math>\leq</math>) 0.6 mmol/L.
 
Once ketone level is less than or equal to (<math>\leq</math>) 0.6 mmol/L, per investigator discretion, subject may start YSI™* FST.
 

○ With observation can occur if subject's glucose is between 60 mg/dL to 300 mg/dL.

Subject Stopping Rules	

● Subject is exhibiting signs and symptoms of DKA (see DKA definition in Section 12.1)

● Severe hypoglycemia (see severe hypoglycemia definition Section 12.1)

● YSI™* glucose greater than (<math>></math>) 500 mg/dL regardless of ketone level

○ For subjects 2-6 year olds, SMBG will be used. All applicable rules related to rescue therapy/low glucose guidelines, will be based on SMBG rather than YSI™*.

● Ketone greater than or equal (<math>\geq</math>) to 3 mmol/L regardless of blood glucose

● Persistent ketone level greater than or equal to (<math>\geq</math>) 1.5 mmol/L after hydration (see ketone management guidelines Section 10.5.4)

● Subject develops nausea, vomiting or abdominal pain

● Maximum blood volume drawn:

○ 4 mL/kg (inclusive of all YSI™* FST days) during this study or 400 cc whichever is more for subjects' age 14-80 years old. However, no more than 2 mL/kg of blood volume in a 24-hour period is to be drawn.

	

○ 3 mL/kg (inclusive of all YSI™* FST days) during this study for subjects' age 7-13 years old.

○ 50 mL will be maximum blood volume for subjects' age 2-6 years old. However, no more than 1 mL/kg of blood volume in a 24-hour period is to be drawn.

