### 8.2.2.6.2. Upon Arrival to the Clinic

Upon arrival to the clinic, subjects would be safe to undergo observation if glucose is between 60 mg/dL to 300 mg/dL.

For subjects who will undergo challenges, ketones are in the range below:

- The start of the YSI™\* FST with challenge can occur if subject's ketone level is less than or equal to ( $\leq$ ) 0.6 mmol/L.

For example, should a subject arrive with ketone levels greater than ( $>$ ) 0.6 mmol/L, per investigator discretion, IV or oral hydration may be provided to subject to bring ketone level less than or equal to ( $\leq$ ) 0.6 mmol/L.

Once ketone level is less than or equal to ( $\leq$ ) 0.6 mmol/L, per investigator discretion, subject may start YSI™\* FST.

- If subject feels ill, then subjects should not fast or delay insulin, but should eat and take insulin as per their usual routine and should not undergo hypo or hyperglycemic challenges that day. They may undergo observation only if the investigator feels it is appropriate.

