## **10. Combined Adult and Pediatric Study Protocol**

### **10.1. Assessment of Safety**

Adverse Event information is collected in this study. See Section 12 for further information on the collection of AEs and safety information.

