### **10.5.3. Ketone Monitoring**

#### **Arrival at the Clinic:**

The start of the YSI™\*/SMBG FST with challenge can occur if subject's ketone level is less than or equal to ( $\leq$ ) 0.6 mmol/L.

For example, should a subject arrive with ketone levels greater than ( $>$ ) 0.6 mmol/L, per investigator discretion, IV or oral hydration may be provided to subject to bring ketone level less than or equal to ( $\leq$ ) 0.6 mmol/L.

Once ketone level is less than or equal to ( $\leq$ ) 0.6 mmol/L, per investigator discretion, subject may start YSI™\*/SMBG FST.

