#### **During Challenge:**

- Glucose greater than ( $>$ ) 300 mg/dL every 60 minutes
- Nausea, abdominal pain or vomiting regardless of glucose level
- Within 30 minutes before the start of any exercise

Note: Should be performed with fingerstick only

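### For ages 2-13, the required exercise at the start of each sampling session depends on glucose alone, and no ketone rule clearly tells sites when to hold it

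*Protocol*

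**What the plan says.** Protocol Section 9.2.2.6.2 (Exercise) makes exercise a requirement for ages 2-13 at the opening of the YSI/SMBG "FST if their glucose is between 100-300 mg/dL mg/dL. They should continue exercise for at least 60 minutes". The only stop conditions given there are low-glucose limits: 70 mg/dL or below at ages 2-6, and 65 mg/dL or below at ages 7-13. The same section has ketones tested on arrival, when glucose exceeds 300 mg/dL, and before discharge, but ties no result to the exercise.

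The ketone rules are elsewhere:

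- **Synopsis, Starting Rules for Subjects.** A session "With challenge can occur if subject's ketone level is less than or equal to" 0.6 mmol/L. A separate line has no ketone condition: "With observation can occur if subject's glucose is between 60 mg/dL to 300 mg/dL".
- **Section 8.2.2.6.2 (ages 14-80).** The limit is introduced this way: "For subjects who will undergo challenges, ketones are in the range below".
- **Section 10.5.3, Arrival at the Clinic.** The "FST with challenge can occur if subject's ketone level is less than or equal to" 0.6 mmol/L.
- **Section 10.5.3, During Challenge.** Ketone checks include one "Within 30 minutes before the start of any exercise", with no limit or action attached.
- **Section 10.5.4.** For a symptom-free subject from 0.6 to below 3.0 mmol/L with glucose up to 500 mg/dL, it calls for hydration and allows in-clinic procedures to go on. Its heading allows investigator discretion.

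Section 9.1 states that ages 2-13 take no part in the glucose challenges. The SAP does not address this point.

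**The concern.** Section 11.1 lists DKA and symptomatic ketosis among the risks of exercise. Its ketone-specific mitigation is to stop challenge procedures when ketones are raised or signs of DKA appear, with a reference to the ketone guidelines. Children aged 2-13 have no challenge procedures to stop, and those guidelines let a symptom-free session proceed below 3.0 mmol/L. So the protocol names the hazard, but its stated protection does not clearly reach the group for whom exercise is compulsory.

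What is at stake is the handling of a symptom-free child who arrives with raised ketones and a glucose inside 100-300 mg/dL. Up to 17 centers take part, and they can reasonably read the text in different ways.

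**Working it through.** There is no figure to recompute. The check is whether any ketone rule holds exercise in a symptom-free child aged 2-13 with glucose of 100-300 mg/dL and ketones above 0.6 and below 3.0 mmol/L.

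| Rule | Place in the protocol | Worded for | Holds exercise in this child? |
|---|---|---|---|
| Exercise start and stop | 9.2.2.6.2 | Ages 2-13 | No; glucose only |
| Ketones at or below 0.6 to start | Synopsis; 10.5.3 | Session with challenge | Unclear; ages 2-13 have no challenge |
| Glucose 60-300 to start | Synopsis | Session with observation | No; glucose only |
| Ketone check before exercise | 10.5.3, During Challenge | Challenges, but any exercise | Unclear; no limit or action |
| Ketones 0.6-1.5 | 10.5.4 | All ages | No; hydrate, procedures allowed |
| Ketones above 1.5 and below 3.0 | 10.5.4 | All ages | No; hydrate, procedures allowed, stop if still above 1.5 after 2 hours of hydration |
| Ketones 3.0 or more, or symptoms | 10.5.4; 10.10.1 | All ages | Outside the range in question; procedures stop |

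Now take a symptom-free child arriving with ketones of 2.0 mmol/L and glucose inside 100-300 mg/dL.

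1. **Narrow reading.** The 0.6 limit is for challenge sessions only. The one start rule not tied to a challenge needs glucose of 60-300 mg/dL, which is met. The session begins, and Section 9.2.2.6.2 then requires exercise. Section 10.5.4 adds hydration, plus insulin if glucose is 250 mg/dL or more, but does not name exercise.
2. **Wider reading.** The 0.6 limit covers every session. The child is hydrated first and the session waits until ketones are 0.6 or below. Exercise begins with the session, so it waits too.

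Both readings are defensible, and they give opposite actions for the same child.

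**The case against.** The strongest reply is that the wider reading is the intended one. Section 10.5.3 sits under the heading "Combined Adult and Pediatric Study Protocol". It names the SMBG session, which only ages 2-6 have, and they have no challenges, so that wording does work only if the limit reaches children. Its last sentence drops the challenge condition: once ketones are at or below "0.6 mmol/L, per investigator discretion, subject may start" the session. Section 10.5.5, written for observation-only subjects, also tells sites to stop the challenge, so Section 10 uses that word loosely. All of this is fair. It makes the scope ambiguous but does not settle it, because the synopsis and Section 8.2.2.6.2 point the other way.

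A second reply is that glucose-only exercise is a consistent design. The observation-only guidelines in Section 8.2.2.6.3 allow ages 14-80 to exercise at 100-300 mg/dL, leave ketone checks to discretion, and send any raised result to Section 10.5.4. Children are tested more strictly, and their exercise may be play. This narrows the gap. But exercise is optional in that older group and compulsory here.

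Third, the range is managed: hydration, investigator discretion in Sections 10.4 and 10.5.4, and stopping rules for symptoms, for 3.0 mmol/L or more, and for ketones that persist after hydration. That also stands. Discretion lets an investigator hold the exercise, but it does not tell sites to do so.

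Finally, the documents give no basis for 0.6 mmol/L as the right limit for play, so the level is a medical decision.

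**Conclusion.** The point holds as a gap in a safety instruction that should be closed. For ages 2-13, exercise is required on glucose alone, and no rule clearly tells sites to hold it in a symptom-free child with ketones above 0.6 and below 3.0 mmol/L.

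A reader might infer more: that these children's raised ketones go unmanaged, or that the protocol directs exercise in a ketotic child whatever the investigator thinks. The documents do not support either. Ketones are tested on arrival, hydration is called for, discretion is allowed, stopping rules apply, and Section 10.5.3 can be read to delay the whole session. Nor do the documents show that harm is likely. They do not say how often children arrive with raised ketones, so the gap can be sized only by its ketone range.

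The conclusion assumes that the narrow reading is one a site could reasonably adopt, and that unpublished site materials, such as the Investigator Site Binder, do not already settle the matter. An instruction there cannot be excluded, but the condition belongs beside the requirement it limits.

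**What to change.** - **Section 9.2.2.6.2, Exercise.** State that exercise begins only if the arrival or pre-exercise blood ketone is 0.6 mmol/L or less (the protocol's own challenge start limit), or another limit set by the medical team. Above it, sampling and hydration continue under Section 10.5.4 without exercise.
- **Section 10.5.3.** Move the check before any exercise out of the During Challenge list so that it plainly covers ages 2-13.
- **Synopsis starting rules and Section 10.5.3.** State whether the 0.6 mmol/L limit applies to sessions without a challenge.

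A separate wording point can be tidied in the same amendment: Section 9.2.2.2 describes exercise at ages 2-13 as a cohort joined at the investigator's discretion, while Section 9.2.2.6.2 makes it compulsory. This does not affect the ketone finding.

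The cost is mainly protocol wording, since the arrival test is already done. There may be one or more extra fingerstick ketone tests when exercise is held for re-testing. Some exercise periods would be delayed or dropped. Because these children have no challenges and Section 7.1 names exercise as a way to obtain low glucose values, some low-range readings may be lost. Sampling itself continues, so the other sensor-reference pairs are kept.

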### **Compression procedure:**

Subjects will be asked to lay on their sensors for at least one hour for each YSI™\*/SMBG FST. Time, duration, and activity will be collected based on sensor location on an eCRF for subjects 7-13 years old (See Table 8) and subjects 2-6 years old (See Table 9) :

**Table 8. Age 7-13 years, Compression Procedure Based on Sensor Wear Location**

Sensor	Guardian™ Sensor (3)		
Location	Arm	Arm	Buttock
Compression Procedure	Subject will be instructed to lay on the arm/ lean on a chair where sensors are inserted.		
OR			
Sensor	Guardian™ Sensor (3)		
Location	Buttock	Buttock	Arm
Compression Procedure	Subject will be instructed to lay on their buttocks where sensors are inserted.		

**Table 9. Age 2-6 years, Compression Procedure Based on Sensor Wear Location**

Sensor	Guardian™ Sensor (3)	
Location	Arm	Arm
Compression Procedure	Subject will be instructed to lay on the arm/ lean on a chair where sensors are inserted.	
OR		
Sensor	Guardian™ Sensor (3)	
Location	Buttock	Buttock
Compression Procedure	Subject will be instructed to lay on their buttocks where sensors are inserted.	
OR		
Sensor	Guardian™ Sensor (3)	
Location	Arm	Buttock
Compression Procedure	Subject will be instructed to lay on the arm/ lean on a chair where sensors are inserted.  OR Subject will be instructed to lay on their buttocks where sensors are inserted.	

**9.2.2.7. Visit 6: Follow-up Phone Call**

The investigational center staff will follow-up with the subject after the YSI™\*/SMBG FST within 24 hours from discharge to address any questions, concerns and ask questions (e.g. most recent blood glucose reading, ketone testing (as applicable), and assessing for AE) to determine how the subject has been doing. In addition, subjects should be reminded to bring medication, syringes, insulin, and infusion sets that might be needed for their personal pumps during the YSI™\*/SMBG FST visit. If subject is unable to be reached, then this should be documented and at least one second attempt to reach subject be performed.

**9.2.2.8. Visit 8: End of Study**

- Visit 7 and Visit 8 may be combined. (e.g., FST occurs on day 7 and end of the sensor wear).
- Investigational center staff will ensure sensor wear time has been met (T=176-188 hours) and the sensor may be removed at that time. It is recommended to have subject remove sensor at clinic to ensure it is removed at proper time.
- Subjects will return to the clinic to address any questions, concerns, and collect adverse events or device deficiencies.
- For subjects who are still wearing the Guardian™ Sensor (3)s, instruct subjects to remove them
- Upload study devices via:
  - CareLink™ Personal For Clinical Research software (CONTOUR®NEXT LINK 2.4 study meter)
  - GST Download Utility Software (Guardian™ Connect Transmitter) following instructions provided
- Perform a Skin assessment on the area of each of the Guardian™ Sensor (3) insertion sites and document in subject source and complete the Skin Assessment eCRFs
- Return all study sensors, devices, unused supplies and study guides from subjects
- An Exit eCRF will be completed at this visit.

## **10. Combined Adult and Pediatric Study Protocol**

### **10.1. Assessment of Safety**

Adverse Event information is collected in this study. See Section 12 for further information on the collection of AEs and safety information.

### **10.2. Replacement Sensors**

#### **10.2.1. Training Period Sensor Wear Rules**

During the training period, if a Guardian™ Sensor (3) dislodges prior to completing, the subject may continue with the remaining sensor(s) until the end of the training period.

#### **10.2.2. Study Period Sensor Wear Repeat Rules**

A subject can replace their **primary** sensor(s) (See Section 15.8.1) once.

Subject will wear the replaced sensors for 7 days and attempt to complete the required YSI™\*/SMBG FST visits.

Please note: It is important for sites to clearly identify the location of the **primary** sensor so that if it falls out, the site does not confuse the **primary** sensor with a companion sensor that may be located close to the primary sensor.

For example, if a primary sensor dislodges the subject should replace all sensors and repeat any FSTs not completed.

- 20 year old subject loses a primary sensor on day 4 and has completed 2 FSTs. Subject should replace **all** sensors and complete the remaining 2 FSTs. Subject does not have to repeat FSTs already completed

For example, if a companion sensor dislodges but the primary sensor is still inserted, the subject should continue with his/her FST schedule.

Scheduling should be performed so that subjects remain in the 90-day window period (i.e. between Visit 1 – Visit 12 for subjects 14-80 years or Visit 1-Visit 8 for subjects 2-13 years).

Subjects will have their YSI™\*/SMBG FST visit rescheduled per the original randomly assigned FST Group.

## 10.3. Repeat Rules for In-Clinic Procedures

- Concurrent failure of both the primary and back-up YSI™\* instruments during YSI™\* FST.
- If subject experiences unresolved IV occlusions during YSI™\* FST requiring fingerstick measurements for a prolonged time period, the in-clinic procedures may be re-scheduled per sponsor recommendation.
- If primary sensor dislodges and FST cannot be completed. Subject should replace all sensors and repeat any FSTs not completed.

## 10.4. Medical Oversight

In order to conduct the glucose challenges, staffing with the appropriate training is required:

- A physician or mid – level provider, such as a nurse practitioner or a physician assistant, who has managed diabetes patients must be available during the entire hypoglycemic and hyperglycemic challenge.
- The Investigator (or designee) will need to have one of the following qualifications; endocrinology fellowship, management in patients with diabetes in a clinical practice or experience running prior studies performing hypoglycemic induction or rescue. The provider must be qualified to treat diabetic emergencies.
- It is assumed that not every subject will meet the desired range or desired time per Hyperglycemic and Hypoglycemic Challenge guidelines. If a subject is unable to meet the desired range for the desired time for either challenge, the challenge still may be viewed as complete.

- Deviation from pre-specified protocol requirements defined in Section 10.5.3 may occur for subject safety per investigator discretion.
- Detailed guidelines for the protocol requirements defined in Section 10.5.3 have been provided to account for diabetes management during study. However, these are guidelines only and investigator discretion may be used.

## 10.5. YSI™\*/SMBG FST Instructions

### 10.5.1. Monitoring During the YSI™\*/SMBG FST

#### Ages 7 - 80 years

The frequency of blood draws for YSI™\* FST sampling is dependent on the value of the previous sample, according to the following ranges:

- less than (<) 75 mg/dL; every 5 minutes (3-8 minutes)
- greater than or equal to (≥) 75 mg/dL; every 15 minutes (7 - 23 minutes)

#### Ages 2 - 6 years

The frequency of blood draws for SMBG FST sampling is dependent on the value of the previous sample, according to the following ranges:

- less than (<) 70 mg/dL; every 5 minutes (3-8 minutes)
- 70-80 mg/dL; every 15 minutes (7 -23 minutes)
- greater than (>) 80 mg/dL; every 30 minutes (maximum of 45 minutes)

### 10.5.2. YSI™\* FST Not Available (For Example, IV Occlusion)

#### Ages 7 – 80 years

In the event that YSI™\* blood glucose values are not immediately available, for safety purposes, the investigational center may use a CONTOUR®NEXT LINK 2.4 study meter to measure glucose. The fingerstick glucose values will be recorded on the appropriate eCRF and not used for analysis.

Venous blood samples should still be drawn for YSI™\* FST.

## **Ages 2 - 6 years**

Subjects ages 2 – 6 years will only do SMBG during their FST. The fingerstick glucose values will be recorded on the appropriate eCRF and will be used for analysis.

### **10.5.3. Ketone Monitoring**

#### **Arrival at the Clinic:**

The start of the YSI™\*/SMBG FST with challenge can occur if subject's ketone level is less than or equal to ( $\leq$ ) 0.6 mmol/L.

For example, should a subject arrive with ketone levels greater than ( $>$ ) 0.6 mmol/L, per investigator discretion, IV or oral hydration may be provided to subject to bring ketone level less than or equal to ( $\leq$ ) 0.6 mmol/L.

Once ketone level is less than or equal to ( $\leq$ ) 0.6 mmol/L, per investigator discretion, subject may start YSI™\*/SMBG FST.

#### **During Challenge:**

- Glucose greater than ( $>$ ) 300 mg/dL every 60 minutes
- Nausea, abdominal pain or vomiting regardless of glucose level
- Within 30 minutes before the start of any exercise

Note: Should be performed with fingerstick only

#### **At Discharge:**

Refer to Discharge guidelines for ketone monitoring in a separate cover.

### **10.5.4. Treatment Guidelines Based on Ketones (Investigator Discretion May Be Used for Medical Management)**

- a) Ketone level greater than or equal to ( $\geq$ ) 0.6 mmol/L and less than ( $<$ ) 3.0 mmol/L with no symptoms of ketoacidosis (nausea, vomiting, or abdominal pain) and for glucose less than or equal to ( $\leq$ ) 500 mg/dL the following should occur:

## For Ketones greater than or equal to ( $\geq$ ) 0.6 mmol/L and less than or equal to ( $\leq$ 1.5) mmol/L

- In-clinic procedures may continue
- Administer oral hydration with sugar free, caffeine free liquids (if subject is able to drink) or IV fluid hydration (if needed):
  - 22 years and older: 100 cc/hour of 0.9 normal saline (NS) for 2 hours
  - 2-21 years rate for IV fluid hydration is 10 cc/kg given over 2 hours.
- If no nausea, vomiting, or abdominal pain, subjects may continue with hydration for a maximum of 2 hours with glucose greater than ( $>$ ) 250 mg/dL with ketones greater than or equal to ( $\geq$ ) 0.6 mmol/L and less than or equal to ( $\leq$ ) 1.5 mmol/L before insulin is administered
- The maximum amount of saline to be infused per kg during the YSI™\* FST is:
  - 60 ml/kg, however it is preferred to have no more than 50 ml/kg for (7 – 80 years).
  - 20 ml/kg for (2 – 6 years).
- For subjects treated with CSII, the catheter should be changed if glucose is greater than or equal to ( $\geq$ ) 250 mg/dL for 2 hours and insulin should be administered with a syringe
- If subjects develop nausea, vomiting, or abdominal pain, the study should be stopped.
- If subject shows signs of fluid overload (i.e., congestive heart failure (CHF), lower extremity edema, crackles on lung auscultation of S3 heart sound) then rate of IV hydration will be decreased to half the current rate

